The anesthesiologist went to the ward one day before the operation to evaluate the anesthesia of the patients who were going to undergo thoracoscopic pulmonary resection, signed the informed consent form, and selected the subjects according to the inclusion criteria and exclusion criteria. They were randomly divided into SAPB & ESPB group(test group) and PVB group(control group). Patients were also taught how to use the spirometer, patient-controlled intravenous analgesia(PCA), and visual analogue scale (VAS). (VAS: a 100 mm horizontal line, with 0 mm at one end of the line, indicating no pain. The other end is 100mm, indicating severe pain. The middle portion indicates varying degrees of pain.)

- 1) All patients were forbidden to drink and eat before operation without preoperative medication
- 2) After the patients entered the operating room, the investigator measured the

VAS score of the patient at rest and coughing in the sitting position. FVC (L), FEV₁ (L) and FEF 25% -75% (L/sec) were measured by spirometer for three times. Patients were assessed preoperatively using the QoR-15 Patient Questionnaire (see attached page).

- 3) Blood pressure, pulse, oxygen saturation and ECG were monitored. Anesthesia induction was performed after mask oxygenation: parecoxib sodium 40 mg, penehyclidine hydrochloride 0.5 mg, tropisetron 2 mg and sufentanil 0.5 μ g \cdot kg $^{-1}$, propofol 1.5–2.0 mg \cdot kg $^{-1}$ and rocuronium 0.8 mg \cdot kg $^{-1}$.
- 4) Performing tracheal intubation, ultrasound-guided radial artery cannulation to monitor ambulatory blood pressure and internal jugular central venous catheterization to establish a central venous channel.
- 5) Ultrasound-guided serratus anterior plane block combined with erector spinae plane block was performed in the experimental group. The erector spinae plane block was performed at T5 and T7 segments, with 10 ml 0.4% ropivacaine in each segment and 20 ml 0.4% ropivacaine in serratus anterior plane block. The control group received ultrasound-guided thoracic paravertebral block at T5 and T7 with 20 ml of 0.4% ropivacaine in each segment.

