10) After returning to the ward, the patient can press the PCA for additional analgesia according to the needs. The patient was given rescue analgesia, a single use of diclofenac sodium suppository, if the pain was not relieved or the patient requested it. Investigators conducted postoperative visits at 2h, 4h, 8h and 24h postoperatively, the dosage of PCA, the times of rescue analgesia, VAS scores at rest and cough and adverse reactions were recorded. FVC (L), FEV1 (L) and FEF 25% -75% (L/sec) were recorded for three times by spirometer in the sitting position at 4h and 24h postoperatively. Patients were assessed postoperatively using the QoR-15 Patient Questionnaire at 24h postoperatively.

6. Outcome measurements

6.1 The primary outcome :

Cumulative morphine consumption at 24h postoperatively

6.2 The secondary outcomes:

- (1) The cumulative morphine consumption at 1h, 2h, 4h and 8h postoperatively.
- (2) The times of remedial analgesia at 1h, 2h, 4h, 8h and 24h postoperatively.
- (3) VAS score at rest and cough at 1h, 2h, 4h, 8h and 24h postoperatively.
- (4) The changes of FVC (L), FEV₁ (L) and FEF 25% - 75% (L / sec) were observed before operation, 1h, 4h and 24h after postoperatively.
- (5) Changes of QoR-15 questionnaire scores before and 24h postoperatively.
- (6) Postoperative complications and rehabilitation time nodes (including drainage tube removal time, discharge time, etc.).

7 Security

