9.3 Reasons for dropout

For any dropout case, the investigator must record the reasons for the dropout. In general, there are five reasons, namely, adverse events, violation of the trial protocol, loss to follow-up (including self-withdrawal of the subject), discontinuation of the sponsor and others.

10. Statistical analysis

Measurement data were analyzed and compared by t-test or Mann-Whitney U test, depending on whether the data were distributed normally or not. Repeated measures data (e.g., morphine consumption, VAS scores, pulmonary function measures) were analyzed using one-way analysis of variance(ANOVA). Enumeration data were compared by χ^2 or Fisher's exact test. $p < 0.05$ was considered significant.

11. Summary of lab report

Unblinding is performed when the statistical analysis is completed and the statistical analysis report is written by the statistical analyst. The statistical analysis report after Unblinding shall be delivered to the main researchers of the experiment to write the research report.

12 Data preservation

The research data related to this clinical trial were kept by the Department of Anesthesiology of Tongji Hospital.

References:

1. Bendixen, M., et al., *Postoperative pain and quality of life after lobectomy via video-assisted thoracoscopic surgery or anterolateral thoracotomy for early stage lung cancer: a randomised controlled trial*. Lancet Oncol, 2016. 17(6): p. 836-844.
2. Kaplowitz, J. and P.J. Papadakos, *Acute pain management for video-assisted thoracoscopic surgery: an update*. J Cardiothorac Vasc Anesth, 2012. 26(2): p. 312-21.
3. Elmore, B., et al., *Pain Management Following Thoracic Surgery*. Thorac Surg Clin, 2015. 25(4): p. 393-409.
4. Kumar, K., et al., *A Review of Opioid-Sparing Modalities in Perioperative Pain Management: Methods to Decrease Opioid Use Postoperatively*. Anesth Analg, 2017. 125(5): p. 1749-1760.

5. Joshi, G.P., et al., *A systematic review of randomized trials evaluating regional techniques for postthoracotomy analgesia*. Anesth Analg, 2008. 107(3): p. 1026-40.
6. Zhu, M., et al., *Ultrasound-Guided Intercostal Nerve Block Following Esophagectomy for Acute Postoperative Pain Relief in the Postanesthesia Care Unit*. Pain Pract, 2018. 18(7): p. 879-883.

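### Section 10 names no baseline covariate for QoR-15 or spirometry, although both are measured before surgery; adding one may improve precision at little cost

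*Combined protocol and SAP*

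**What the plan says.** Baselines are collected. Section 5, item 2, states "Patients were assessed preoperatively using the QoR-15 Patient Questionnaire (see attached page", and records that FVC, FEV1 and FEF25-75 "were measured by spirometer for three times" before induction. Resting and coughing VAS are scored at the same visit. Spirometry is repeated at 1 h (item 9), and item 10 says the values "were recorded for three times by spirometer in the sitting position at 4h and 24h postoperatively". QoR-15 is repeated at 24 h.

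Section 6.2 lists the outcomes. Item 4 is the changes in the three lung function measures, which "were observed before operation, 1h, 4h and 24h after postoperatively". Item 5 is "Changes of QoR-15 questionnaire scores before and 24h postoperatively". Item 3, by contrast, gives postoperative values only: "VAS score at rest and cough at 1h, 2h, 4h, 8h and 24h postoperatively".

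Section 10 offers two sentences for continuous data. The first is "Measurement data were analyzed and compared by t-test or Mann-Whitney U test, depending on whether the data were distributed normally or not". The second is "Repeated measures data (e.g., morphine consumption, VAS scores, pulmonary function measures) were analyzed using one-way analysis of variance(ANOVA", which names pulmonary function. QoR-15 is in neither, and could fall under the first sentence or under the open list of examples in the second. No covariate is named in section 10 or anywhere else in the protocol.

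**The concern.** When an outcome has a value before treatment, a randomised comparison can use it in three ways: ignore it (raw postoperative value), subtract it (change score), or adjust for it (ANCOVA). All three estimate the group difference without bias, but their precision differs. ANCOVA estimates the slope on baseline from the data, whereas the other two fix it at 0 or 1. Apart from a small estimation cost, ANCOVA is therefore never the least precise of the three.

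The protocol collects the baselines but does not say which of the three applies, so the choice is left to the analyst. Recovery is in the trial's title, and QoR-15 and lung function are the recovery-related secondary outcomes that have a baseline; drain removal and discharge times have none. Section 3.2 claims power only for 24 h morphine, so precision obtainable from data already in hand may be useful for these outcomes.

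**Working it through.** **The plan's own figure.** Section 3.2 gives pilot SDs of 4.8 and 4.2 mg, a difference of 2.5 mg, one-sided 0.05 and 80% power.
- Pooled SD = √[(4.8² + 4.2²)/2] = 4.51.
- n per group = 2 × (1.645 + 0.842)² × 4.51² / 2.5² = 40.2, so 41, as stated.
- 41/0.9 = 45.6, so 46 per group and 92 in total, as stated.

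This calculation concerns morphine, which has no preoperative value, so nothing below alters it. It supplies N = 82 analysed.

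**Set-up for an outcome with a baseline, at one postoperative time point.** Take the postoperative SD as 1, the baseline SD as k, and the baseline-to-postoperative correlation as ρ. The documents give neither k nor ρ; both are assumptions shown over a range. Relative variances of the group difference are:
- raw postoperative value: 1
- change score: 1 + k² − 2ρk
- ANCOVA: (1 − ρ²) × c, with c = 1 + 1/(82 − 4) = 1.0128, the expected cost of estimating one slope.

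**Worked case, k = 1, ρ = 0.7.** ANCOVA: 0.51 × 1.0128 = 0.5165. Change score: 1 + 1 − 1.4 = 0.60. The ratio is 0.861, a reduction of 13.9%. Against the raw value the reduction is 1 − 0.5165 = 48.3%.

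**Net variance reduction from ANCOVA**

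| Comparator | ρ = 0.5 | ρ = 0.7 | ρ = 0.8 |
|---|---|---|---|
| Change score, k = 0.7 | 3.8% | −1.3% | 1.5% |
| Change score, k = 1 | 24.0% | 13.9% | 8.8% |
| Change score, k = 1.3 | 45.4% | 40.6% | 40.2% |
| Raw value, any k | 24.0% | 48.3% | 63.5% |

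A simulation of 40,000 trials with 41 per group agrees. The ANCOVA-to-change variance ratios at ρ = 0.5, 0.7 and 0.8 were:
- k = 1: 0.761, 0.858, 0.913
- k = 0.7: 0.959, 1.012, 0.987
- k = 1.3: 0.549, 0.596, 0.594

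The ANCOVA-to-raw ratios (k = 1) were 0.760, 0.516 and 0.366.

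**Where the gain disappears.** Against a change score, the gain before the slope cost is nil when ρ = k, because the best slope (ρ/k) is then exactly 1; the net loss is the 1.3%. Against the raw value, break-even is ρ = √(1 − 1/1.0128) ≈ 0.11. For VAS, preoperative pain may vary little and correlate weakly with later pain: the reduction against raw values is −0.3% at ρ = 0.1 and 2.8% at ρ = 0.2.

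**Why the wording in section 6.2 can stay.** If postoperative Y = a + g·group + b·baseline + error, then Y − baseline = a + g·group + (b − 1)·baseline + error. The group difference g is the same in both.

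**The case against.** The strongest reply is that nothing in the plan is wrong. Unadjusted randomised comparisons are valid, the outcomes are secondary and unpowered, and section 6.2 suggests change scores, which already use the baseline. On that reading the change-score rows of the table are the relevant ones, and they run from about −1% to 45%, depending on two quantities that the documents do not give. This stands, and it is why the point is an optional improvement and not an error.

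The figures are also for a single time point, whereas section 10 places lung function under repeated measures. That stands too: no gain is claimed here for a model that combines time points, and the numbers apply most directly to QoR-15 at 24 h.

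Two further objections carry less weight. ANCOVA would displace the Mann-Whitney route for non-normal data, but a specific instruction for named outcomes takes precedence over the general sentence, and the text can say so. Adjusting QoR-15 once and three lung function measures at three times makes 10 comparisons (3 × 3 + 1), but the covariate changes the model for each comparison and adds none.

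The lack of a rule for combining the three spirometer readings is a separate gap that matters with or without a covariate. It lends no weight to this point, nor does VAS. Whether one-way ANOVA suits repeated measures, and the normality-based switch of test, are also separate questions.

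**Conclusion.** The point holds as a free improvement to secondary outcomes only. The baselines are collected, no covariate is named, and the choice between change and raw value is open. Under the assumed range, adjustment at one time point with N = 82 saves between about nil and 45% of the variance against a change score, and 24% to 63.5% against the raw value. The greatest expected loss is about 1.3%, so the possible gain clearly outweighs the possible cost. The actual size cannot be fixed from the documents, because it rests on ρ and k, and confidence in a material gain is medium. There is no bias, and no effect on the primary outcome, the type I error rate or the sample size.

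**What to change.** In section 10, prespecify that the between-group comparisons of QoR-15 at 24 h, and of FVC, FEV1 and FEF25-75 at 1, 4 and 24 h, include the matching preoperative value as a covariate. This can be ANCOVA at each time point, or the same covariate in whatever repeated-measures model is chosen. Report adjusted group differences with 95% confidence intervals. State that for these outcomes this instruction replaces the general t-test/Mann-Whitney and one-way ANOVA sentences.

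State one rule for reducing the three spirometer readings to a single value and apply it before and after surgery, since the covariate needs a defined value. Adjusting VAS for its baseline is optional.

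The cost is a few sentences of wording and one degree of freedom in each single-time-point model. At N = 82 that is about 1.3% of variance, and the two-sided 5% critical value moves from 1.9901 to 1.9905. No new data, visits or patients are needed.
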